#### 2.16.6 Analysis of Safety Variables

Safety will be assessed through the degree of pain/discomfort related to the procedure (universal pain scale) and the collection of Adverse Events throughout the course of the study. For each treatment group these variables will be summarized. The summaries will include the number and percent of patients for each outcome. No statistical comparisons will be performed for any of these variables.

## **3.0 RISK ANALYSIS AND MANAGEMENT**

#### 3.1 Risk Determination

This device study used in this study does not meet the FDA definition for a Significant Risk Device study per 21 CFR 812.3(m). Therefore, the sponsor determines that this is a non-significant risk device study.

Significant risk device means an investigational device that:

(1) Is intended as an implant and presents a potential for serious risk to the health, safety, or welfare of a subject;

(2) Is purported or represented to be for a use in supporting or sustaining human life and presents a potential for serious risk to the health, safety, or welfare of a subject;

(3) Is for a use of substantial importance in diagnosing, curing, mitigating, or treating disease, or otherwise preventing impairment of human health and presents a potential for serious risk to the health, safety, or welfare of a subject; or

(4) Otherwise presents a potential for serious risk to the health, safety, or welfare of a subject.

#### 3.2 Risk Management

The Investigator in this clinical trial has been invited to participate based on his/her previous experience with the use of the system and/or similar systems and industry experience. Experience with treatments is the most critical element in managing subject risk in this trial.

In addition, as with any study, there is a risk of bias. Objective evaluation methods may be used in conjunction with subjective evaluation methods when feasible. The value of the compensation to the clinical investigator for conducting the study is not influenced by the study outcome. If photographic results are listed as the primary objective, they are to be evaluated by blinded evaluators who did not partake in the study. If information concerning investigator assessment of improvement or investigator satisfaction is collected, then it is not listed as an objective for the study.

All other known risks will be disclosed to the subject via the informed consent process. Since this is an elective procedure and the subjects are volunteers, it can be assumed that their signature on the informed consent is indicative of their agreement to accept the risks involved.

The risks to the subjects who participate in this study are the same as those for the subject undergoing similar ablative radiofrequency treatments. It is possible to have an adverse reaction to the PotenzeTM device use. There may be some side effects that we don't know about yet.

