## **1.2 Objectives**

- 1. Primary Objectives:
  - Assessment of safety of the study device through the collection of side effects throughout the study.
  - Assessment of the efficacy of the study device through Investigator and subject satisfaction.
  - Evaluation of baseline photographs compared to post treatment images.
- 2. Assessments:
  - Treatment discomfort evaluation
  - Subject treatment experience questionnaire
  - Clinician ease of use questionnaire
  - Clinician and subject satisfaction questionnaire
  - Treatment area photograph blinded evaluation
  - Baseline and short-term histological tissue response as seen in biopsies.

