## 2.0 PROTOCOL

## 2.1 Protocol Methodology and Analysis

## Methodology:

Subjects are to be enrolled in this clinical study if they are 18 - 55 years old. Up to 120 subjects will be enrolled at 5 study centers. Subjects may receive up to 5 treatments with the PotenzaTM device if they present with conditions such as, but not limited to; Wrinkles, fine lines, crepey skin, acne scars, active acne, enlarged pores, stretch marks, or loose skin on the face, neck and/or body.

Subjects will attend a screening/pretreatment visit which may be performed on the same day as the treatment visit. Subjects will receive up to 5 treatments. All subjects may receive a phone call or attend a visit 24 hours post each treatment and will receive a phone call or attend a visit 1 week (2-10 days) after each treatment to record side effects. Subjects will be required to return for a follow-up visit 30 days after the final treatment. Subjects may also attend an optional follow up visit 90 days after the final treatment. An unscheduled visit or phone call may be performed at any time during the study at the request of the subject or as deemed necessary by the site Investigator.

Analysis:

Upcoming generations are proving to have an interest in aesthetic dermatology treatments and will drive demand for innovated products, procedures, and practice design. Due to this shift in patient base, practices need to evolve to adapt to the newer generational ideologies. There have been rapid advances in RF technology over the past few years and the nonsurgical treatment using this energy source offers great promise to our aging population. Radiofrequency micro needling technology for the treatment of dermatologic conditions needs to be further investigated to optimize treatment parameters for safe and effective non-ablative treatments.

Relevance: Does not apply to this study – feasibility study.

Testability: Does not apply to this study – feasibility study.

Compatibility: Does not apply to this study – feasibility study.

Predictive power: Does not apply to this study – feasibility study.

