## 2.2 Protocol Study Design

This is a prospective, open label, multi-center clinical study

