#### **Physician Questionnaire:**

The Clinical Global Aesthetic Improvement Scale (CGAIS) ranging from "worse" to "very much improved" will be used to judge the improvement as seen by the treating Investigator.

Global Aesthetic Improvement Scale Assessment				
Rating	Description			
1	Very Much Improved- Optimal cosmetic result in this subject			
2	Much Improved- Marked improvement in appearance form the initial			
2	condition, but not completely optimal for this subject.			
2	Improved- Obvious improvement in appearance from initial condition, but a			
3	re-treatment is indicated.			
4	No Change- The appearance is essentially the same as the original condition.			
5	Worse- The appearance is worse than the original condition.			

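### Section 3.2 says investigator ratings are not an objective, yet efficacy rests on them, and the blinded photograph reading is given an analysis that cannot be applied to it

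*Combined protocol and SAP*

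**What the plan says.** **On investigator ratings.** Section 3.2 (Risk Management) acknowledges a risk of bias and then gives assurances. One is: "If information concerning investigator assessment of improvement or investigator satisfaction is collected, then it is not listed as an objective for the study". Another is: "If photographic results are listed as the primary objective, they are to be evaluated by blinded evaluators who did not partake in the study".

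Section 1.2 lists among the primary objectives "Assessment of the efficacy of the study device through Investigator and subject satisfaction" and "Evaluation of baseline photographs compared to post treatment images". The photograph objective does not mention blinding. "Treatment area photograph blinded evaluation" stands separately, under Assessments.

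Section 2.16.1 makes study success depend on investigator and subject satisfaction rates of at least 80%, together with a side effect profile acceptable to the physician. Section 2.16.5 names the physician-graded CGAIS at Visit 8 as the primary efficacy variable. Section 2.14 says that this scale "will be used to judge the improvement as seen by the treating Investigator". Section 2.2 describes the design: "This is a prospective, open label, multi-center clinical study".

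**On the photographs.** Section 2.14 (Blinded Evaluation) plans three blinded independent dermatologists, trained beforehand, who pick out the pre-treatment image. Section 2.16.5 makes image-based variables secondary, leaves them to be fixed later, and gives them the same analysis as the CGAIS. Section 2.16.1 counts a secondary objective as met if its assessment is statistically significant or reaches an 80% response rate.

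**The concern.** There are two separate defects.

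First, the plan gives its readers an assurance about bias that its own objectives contradict. Anyone relying on Section 3.2 would believe that the efficacy conclusion does not rest on the treating investigator's opinion. It does.

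Second, in an open-label study with no comparison group, the blinded reading is the efficacy evidence best protected from rater expectation. Its role is inconsistent: photograph comparison is a primary objective in Section 1.2, but image variables are secondary in Section 2.16.5. Its assigned analysis cannot be carried out. A result could therefore depend on choices the plan leaves open: how three readers become one result, what the chance level is, and which of the two success routes counts.

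**Working it through.** **1. The assurance against the rest of the plan (no arithmetic).**

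- Is the condition in Section 3.2 met? Yes. Sections 2.9, 2.13 and 2.14 collect physician questionnaires and the CGAIS.
- Is such information listed as an objective? Yes. Section 1.2 lists investigator satisfaction as a primary objective, and this alone contradicts the assurance.
- Is it incidental? No. Section 2.16.1 makes it a success condition, and Section 2.16.5 makes the investigator's CGAIS score the primary efficacy variable. A variable is not literally an objective, but it is how the efficacy objective is tested.

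**2. The inherited analysis against the reading task.**

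| Element of Section 2.16.5 | Applied to identifying the pre-treatment image |
|---|---|
| Change from baseline | Undefined: the reading compares baseline with follow-up, so it has no baseline value |
| Mixed model for that change | Undefined for the same reason |
| Treatment-group comparison | The design describes no treatment groups |
| Paired t-test | No pair of values to difference |
| Number and percent for categorical variables | Fits, but gives no test, chance level or reader rule |

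**3. What the open choices are worth.** The plan's 120 (Section 2.16.2, including departures) comes without effect size, rate or power, so it cannot be reproduced. Assumptions here: one pre/post pair per subject, a two-image choice with 50% chance, and 120 readable pairs (108 and 96 where 10% or 20% are lost). Significance is two-sided at 0.05, as in Section 2.16.5.

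*Success route.* The exact binomial test needs the smallest k with 2·P(X ≥ k | n, 0.5) < 0.05.

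- n = 120: k = 72 (p = 0.035; 71 gives 0.055). n = 108: k = 65. n = 96: k = 59.
- 80% route: 0.8 × 120 = 96; 87 of 108; 77 of 96.
- At 72/120 (60%) the exact 95% CI is 50.7% to 68.8%, which excludes 80%.

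| True subject-level rate (n = 120) | P(X ≥ 72) | P(X ≥ 96) |
|---|---|---|
| 65% | 89% | <1% |
| 70% | 99% | 1% |
| 75% | >99% | 12% |
| 80% | >99% | 55% |

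*Combining readers.* Let ρ be the between-reader correlation (assumed; beta-binomial), s = (1 − ρ)/ρ and b = s/2. Under guessing, P(no reader correct) = b(b+1)(b+2)/[s(s+1)(s+2)], or 0.5³ = 0.125 at ρ = 0. For example, ρ = 0.2 gives s = 4, b = 2 and 24/120 = 0.20, so at least one reader is correct for 80% of subjects. For 2-of-3 with a 70% reader rate and ρ = 0, the subject rate is 0.7³ + 3 × 0.7² × 0.3 = 0.784.

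| n = 120 | ρ = 0 | 0.2 | 0.5 | 0.8 |
|---|---|---|---|---|
| Guessing, any one reader correct: P(X ≥ 96) | 0.99 | 0.55 | 0.004 | about 2 in 10⁷ |
| 70% reader rate, 2-of-3: P(X ≥ 96) | 38% | 10% | 2% | 1% |
| 360 readings pooled as independent: upper-tail error | 2.0% | 4.1% | 7.3% | 10.1% |
| Same, two-sided | 4% | 8% | 15% | 20% |

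The pooled rows reject at 200 or more, or 160 or fewer, of 3 × 120 = 360 readings. The plan proposes neither an any-one rule nor pooling; it excludes neither. Under 2-of-3, guessing gives 50% per subject at every ρ by symmetry, so a subject-level exact test keeps its error rate.

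**The case against.** - **This is a "feasibility study" (Section 2.1).** True, and it limits severity. But the plan still sets success criteria and 0.05 tests, so it should say how they apply.
- **The figures do not measure the contradiction.** This stands. Every number above concerns the blinded reading. None sizes the effect of relying on an unblinded rater.
- **The most striking figure is an extreme case.** This stands. The 0.99 needs three fully independent guessers and a rule nobody has proposed; it falls to 0.55 at ρ = 0.2 and is negligible at 0.8. Likewise, half of the two-sided pooled error is readers doing worse than chance, so the upper-tail row is the rate of false efficacy claims.
- **Section 2.16.5 does provide something usable.** In part: the number-and-percent summary fits, which narrows the gap without closing it.
- **A reader might infer that image variables will be picked once results are known.** The text does not establish this. Section 2.16.5 can equally mean that variables based on image grading will be defined later. What is supported is that they are not pre-specified.
- **A reader might also infer that Section 3.2's rule on photographs is broken.** It is not: Section 2.14 supplies blinded independent reviewers.

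**Conclusion.** Both defects hold as the plan is written and should be fixed. The assurance in Section 3.2 is contradicted directly by Section 1.2, and Sections 2.16.1, 2.14 and 2.16.5 make the investigator's rating decisive in an open-label study. The analysis assigned to image variables is undefined for the only image task described.

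For the blinded reading, the two success routes set very different bars: 60% against 80% correct at 120 pairs, and a 99% against 1% chance of passing at a true 70%. This rests on the assumed two-image choice and one pair per subject. The effect of the reader rule depends strongly on between-reader correlation, which the documents do not give, so it should be read as a range. None of this shows that the sponsor intends a favourable rule, or that the CGAIS result would be wrong; it shows that the plan does not prevent the ambiguity.

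**What to change.** **Reconcile Sections 1.2, 2.16.1, 2.16.5 and 3.2.** Either make investigator satisfaction and the CGAIS supportive, or withdraw the assurance in Section 3.2 and state that the efficacy conclusion rests on an unblinded rater.

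**Define the Visit 8 blinded reading before any image is graded:**

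- One pre-specified image pair per subject, with a named area if several are treated (Section 2.1 allows face, neck and/or body), and image order randomised.
- The subject as the unit, with a fixed reader rule such as at least 2 of 3 correct.
- Whether the reading is primary or secondary, and which route in Section 2.16.1 decides success.
- In place of the inherited analysis, an exact binomial test against the stated chance level, with the proportion and its exact CI.
- A statement that using only readable Visit 8 pairs is narrower than two existing rules: the intention-to-treat set in Section 2.16.3, and the exclusion in Section 2.16.5 of patients with no post-baseline assessment. Section 2.13 also schedules 1-week questionnaires and photographs, so a patient without Visit 8 data can still have a post-baseline assessment. Report the number missing, and add missing-as-incorrect in all treated subjects as a sensitivity analysis.

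**Cost.** Wording only; the readers and Visit 8 photographs are already planned. Power of the readable-pairs test at a true subject-level rate of 65% is 89%, 87% and 80% with 120, 108 and 96 pairs; at 70% it is 99%, 99% and 97%. The headline may be less favourable. Identification shows neither the direction nor the size of change, so the CGAIS should still be reported.

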#### 3.3 Risk Analysis

#### CONTEXT OF THE PROPOSED INVESTIGATION:

Radiofrequency (RF) technology is commonly used in surgery, noninvasive treatments and aesthetic applications. RF technology combined with micro needling is a safe method for non-ablative (A non-wounding device treatment which heats underlying skin) treatment because energy can be precisely delivered through the skin to the dermal tissue beneath with minimal injury to the epidermis.

Aging skin shows decreased collagen synthesis and alteration of fiber networks. By gently heating dermis tissue (which is comprised of collagen, elastic fibers and ground substance), both immediate effects (collagen contraction) and long-term effects (wound-healing response with neocollagen production) will occur. RF-induced thermal injury to the dermal tissue will produce a microinflammatory response to induce collagen denaturation, contraction, and subsequent synthesis as well as elastin and ground substance production.iii Microneedling will cause discrete coagulative injury in the dermis while sparing the epidermis. This allows for a faster healing time and fewer complications in the treatment area.

The extent of collagen shrinkage, fibroblast activation, fibroplasia and neocollagenesis in the different skin layers is based on a complex multivariate mechanism, which depends on the

temperature distribution and timing. Further investigation of parameter optimization is necessary to achieve safe and efficacious results.

#### ASSESSMENT OF RISKS OF THE PROPOSED INVESTIGATION:

There are two risks identified with the Potenza™ device used in this study. The first risk identified is the efficacy of the treatment. There is a lack of clinical data for evidence of effectiveness when treating with the Potenza™ device. The second risk identified is the safety profile of the device.

The risk identified with the overall clinical investigation is the integrity of the data collected.

There are multiple clinical mitigation strategies for the risks identified. Proper training on the device and protocol will be performed. Data from other comparable devices, such as the Lutronic Genius and Infini and Genius Vivace, will be utilized to minimize side effects and optimize treatment outcomes. Monitoring of the study will be implemented to minimize subject and data risks.

ASSESSMENT OF BENEFITS OF THE PROPOSED INVESTIGATION: The subject may or may not have a reduction in the condition they present with.

#### CONSIDERATION OF PATIENT PREFERENCE INFORMATION:

Many physicians support the use of radiofrequency devices minimally invasive cosmetic treatments due to current patient satisfaction of cosmetic results with the currently available devices. However, there is still a level of interest in novel technologies that could reduce the need for future treatments.

#### ASSESSMENT OF UNCERTAINTY:

There is uncertainty of the safety and efficacy of the treatment with Potenza™ since it is not cleared for use by the FDA.

#### CONCLUSION:

The PotenzaTM device is intended for electrocoagulation and hemostasis of soft tissues for dermatologic conditions. This device is determined to be a non-significant risk study. The risks posed to the subjects and integrity of data are acceptable.

Patient population to be enrolled in this clinical study: Total anticipated population: 120 Subjects Age Range years old: 18 – 55 Years Old Gender: Male or Female Condition: Such as, but not limited to; Wrinkles, fine lines, crepey skin, acne scars, active acne, enlarged pores, stretch marks, or loose skin on the face, neck and/or body.

#### 4.0 DEVICE DESCRIPTION AND SPECIFICATIONS

The PotenzaTM device was FDA cleared for use on February 20th, 2020 (K192545). The Potenza device is intended for use in dermatologic and general surgical procedures for electrocoagulation and hemostasis.

This study is considered investigational because this device may not be used within its currently cleared instructions for use.

Model/Class	POTENZA / IIb			
Input Rating	100-240V, 50/60Hz, 500VA			
Applied Frequency	1 & 2MHz			
Maximum Power	MOTOR Handpiece			
	Min1~Max50Watt, Rf Time=5~990ms, Output Voltage:0~100V(Load			
	200Ω)			
	SOLENOID Handpiece			
	Min1-Max50Watt, Rf Time = 5~400ms, Output Voltage:0~100V(Load			
	200Ω)			
	AC Handpiece			
	Min1-Max40Watt, Rf Time = 5~990ms, Output Voltage:0~80V(Load			
	200Ω)			

The PotenzaTM Device Specifications are:

The PotenzaTM device Operator Manual: Attachment I

The PotenzaTM consumables are: Tips, NEM Pads

#### 5.0 MONITORING PROCEDURES

The Sponsor Standard Operating Procedure (SOP) for monitoring the investigative site will be followed. The sponsor will train the site following sponsor SOP's and may be present at initiation of treatment. The sponsor will also monitor the site periodically. The Investigator/Institution will permit trial-related monitoring, audits, IRB/IEC review, and regulatory inspections by providing direct access to source documents. The sponsor may request intermediate data following each visit to evaluate treatment progress. Case Report Forms will be reviewed for current data and Regulatory Binders will also be reviewed for correct documents. The sponsor will collect data at the end of the follow up period. The sponsor will list the study on clinicaltrials.gov when required by FDA regulations.

The monitoring plan for this study is outlined in the Cynosure Monitoring Plan.

ASSIGNED CLINICAL RESEARCH MONITOR: Monitor #1 Name: [name] Institution: Cynosure, LLC Address: [name]

#### 6.0 LABELING

Sample labeling will follow FDA regulations and the sponsor standard operating procedure. If applicable, the PotenzaTM device label will include, (in accordance with 801.1):

Statement: "CAUTION--Investigational device. Limited by Federal (or United States) law to investigational use."

Additionally, the label or other labeling will describe all relevant contraindications, hazards, adverse effects, interfering substances or devices, warnings, and precautions.

Directions for use are contained in the PotenzaTM Operators Manual

#### 7.0 CONSENT MATERIALS

Forms and informational materials which are provided to the subject during the informed consent process are listed below:

Form/Informational Material				
Description				

Pre and Post Treatment Instructions

Informed Consent Form

#### 8.0 INSTITUTIONAL REVIEW BOARD INFORMATION

This protocol, informed consent forms, and any amendments to the protocol will be reviewed by the appropriate Institutional Review Board prior to initiation. The study will not be initiated without the approval from the Institutional Review Board.

#### 9.0 OTHER INSTITUTIONS

If a part of the study is conducted by an institution that has not previously been identified within the Investigational plan each institution's contact information will be documented below;

No other institutions will be part of this study.

## 10.0 ADDITIONAL RECORDS AND REPORTS

If this is an IDE study, additional records and reports will be maintained on the investigation in addition to those prescribed in 21 CFR 812 sub-part G. If this is a non-IDE study, the study summary will be maintained on the investigation and may include those prescribed in 21 CFR 812 sub-part G.

Report	Submit To	Description/Constraints
N/A	N/A	This is a non-IDE study; no additional records or reports will be maintained.

## 11.0 PREGNANCY

Females may not participate in this study if they are pregnant, breastfeeding, were pregnant within the last three months or are planning a pregnancy during the study.

If the subject thinks they have become pregnant during the study, it is important that they inform the Investigator immediately. If she becomes pregnant or thinks that she may be pregnant, she will be removed from the study and will be asked to perform a final evaluation similar to that of the final follow-up visit. The Investigator may request to track the pregnancy and will report the pregnancy to the Sponsor.

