#### 2.6 Pre-Treatment Procedures

If the subject is of childbearing potential (i.e. females not post-menopausal or not surgically sterile), then they will be asked if they are pregnant, the date of their last menstrual cycle, and perform a pregnancy test. If the treatment is on the abdomen, a urine pregnancy test must be performed before each treatment. A urine pregnancy test may be conducted at the Investigators discretion during the study. If a urine pregnancy test is conducted, then a negative result must be obtained within 24 hours prior to the treatment.

Urine Pregnancy Test Procedure:

- 1. A urine sample is tested mid-stream or by cup sample with an indicator stick.
- 2. Negative results are indicated on the indicator stick.
- The following Pre-Treatment instructions will be reviewed:
  - Remove all jewelry and makeup, including eye makeup, lotions or sun block and wash facial area prior to treatment.
  - For an optimum treatment, keep hydrated by drinking water (at least 8 cups daily) or hydrating fluids, such as Gatorade, and avoid drinking alcohol for several days in advance.
  - For five to seven days prior to treatment, at the physician's discretion, avoid therapies that may cause erythema (redness) or irritation such as Retin A or products containing Isotretinoin, glycolic and or salicylic acid.
  - Shave visible hair from the treatment area. Male beards should be shaved day of treatment. RF follows the path of least resistance and the hair will receive the energy.
- Photographs will be taken prior to the first treatment.

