## **12.0 SUBJECT WITHDRAWAL**

The subject is free to withdraw from this study at any time. The subject must inform the Investigator immediately if they intend to withdraw. To terminate the subject's participation in this study, they must contact the Investigator at the contact information listed on page one of the informed consent form. They will be asked to come to the study clinic or Investigators office to complete a final follow up visit and may be asked to perform end of study procedures. Their decision to participate in this study or to withdraw from this study will not influence the availability of their future medical care and will involve no penalty or loss of benefits to which they are otherwise entitled.

The Investigator in charge of the study can remove the subject from this study without their consent for any reason, including, but not limited to:

- a) His/her judgment that any condition or circumstance may jeopardize their welfare or the integrity of the study.
- b) Their failure to follow the instructions of the Investigator(s).
- c) If the study is stopped by the sponsor and/or Investigators participating in the study prior to completion.

Data collected prior to withdrawal will be used in data analysis but after withdrawal no further data will be collected.

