- Highly Probable The event follows a reasonable temporal sequence from the time of investigational product administration; and follows a known response pattern to the investigational product; and cannot be reasonably explained by other factors such as the subject's clinical state, therapeutic interventions, or concomitant medications administered to the subject; and either occurs immediately following investigational product administration, or improves on stopping the investigational product, or reappears on repeat exposure, or there is a positive reaction at the application site.

Each adverse event reported will be graded on a 3-point severity. Using the following definitions for rating severity will be used:

- Mild easily tolerated, causing minimal discomfort, and not interfering with normal everyday activities.
- Moderate sufficiently discomforting and may interfere with normal everyday activities.
- Severe incapacitating and/or preventing normal everyday activities.

A Serious Adverse Event (SAE) is any adverse device experience that results in any of the following outcomes: death, a life-threatening adverse device experience, in-patient hospitalization or prolongation of hospitalization, a persistent or significant disability/incapacity, or a congenital anomaly/birth defect. Important medical events that may or may not result in death, be life-threatening, or require hospitalization may be considered a serious adverse device experience when, based upon appropriate medical judgment, they may jeopardize the subject or subject may require medical or surgical intervention to prevent one of the outcomes listed in this definition

If any of the above adverse events are serious as defined by the FDA Code of Federal Regulations (CFR), Title 21, special procedures will be followed. All serious adverse events will be reported within 24 hours of acknowledgment to the Sponsor whether or not the serious events are deemed sampling session related. All serious event reporting will adhere to 21 CFR part 812 and the IRB will be notified accordingly.

The SAE information will be entered into the database and a desk copy of the complete SAE report will be submitted to the study file.

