Adverse events, whether serious or non-serious, will be followed until the condition is resolved, stabilized, otherwise explained or the subject is lost to follow-up. Adverse events will be captured throughout the study and where appropriate, medical tests and examinations will be performed to document the resolution of event(s). Outcomes may be classified as resolved, improved, unchanged, worse, fatal, unknown or lost to follow-up. Following the resolution of any study-associated adverse events there will be no further adverse event reports for that subject.

Report	Submit To	Description/Constraints
Adverse Events, Unanticipated Adverse Device Effect	IRB and Sponsor	If an unforeseen complication is determined to be an unanticipated adverse device effect, the investigator's report must be submitted within 10 working days after the investigator first learns of the effect.
Serious Adverse Events	IRB and Sponsor	The sponsor must be notified within 24 hours of serious adverse events. The IRB must be notified within 10 working days of serious adverse events as defined by FDA guidelines.

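### Birth defect is a serious adverse event criterion, but following a pregnancy to its outcome is optional, so an absence of such reports cannot be interpreted without the number followed

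*Combined protocol and SAP*

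**What the plan says.** Section 14.0 includes in its list of serious outcomes "a persistent or significant disability/incapacity, or a congenital anomaly/birth defect". On timing it says: "All serious adverse events will be reported within 24 hours of acknowledgment to the Sponsor".

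Section 11.0 states: "If she becomes pregnant or thinks that she may be pregnant, she will be removed from the study". One final evaluation is requested, and the section then says: "The Investigator may request to track the pregnancy and will report the pregnancy to the Sponsor".

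Section 12.0, which covers both withdrawal by the subject and removal by the Investigator, says that "after withdrawal no further data will be collected".

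Section 14.0 also has a follow-up rule: "Adverse events, whether serious or non-serious, will be followed until the condition is resolved", with stabilisation, another explanation or loss to follow-up as the alternatives. It then ends adverse event reporting for a subject once her study-associated events have resolved.

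On detection during treatment, Section 2.6 says: "If the treatment is on the abdomen, a urine pregnancy test must be performed before each treatment". The footnote to the schedule in Section 2.13 confirms that repeat verification is required only for abdominal treatment, although Section 2.6 allows a test at the Investigator's discretion at any time.

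**The concern.** A birth defect is normally known only at or near the end of a pregnancy. Participation lasts at most nine months (Section 1.3), so a pregnancy conceived on study would ordinarily end after the subject has left. Such an outcome reaches the safety data only if somebody is told to go and find it, and nobody is. The 24-hour reporting duty does not help, because its clock starts when the event becomes known.

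Safety is the first-listed primary objective (Section 1.2). With tracking left to choice at five centers, the number of birth-defect reports would depend partly on which Investigators asked. A report stating that none occurred would have no known denominator.

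**Working it through.** The documents give no figure for pregnancies, pregnancy outcomes or contraceptive failure, so there is no planned number to reproduce. The check has three parts.

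**1. The rules side by side**

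- Fact of pregnancy: must go to the Sponsor (11.0).
- Outcome of pregnancy: may be tracked, at the Investigator's choice (11.0).
- Data after withdrawal: none collected (12.0). Read literally, this blocks even the optional tracking in 11.0.
- Follow-up to resolution: applies to adverse events (2.15 and 14.0). No section defines pregnancy as an adverse event, so this rule does not reach it.
- End of reporting: once study-associated events have resolved (14.0). A removed subject with no open event could be closed long before delivery.

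No section requires the outcome to be obtained.

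**2. How many pregnancies are at issue**

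Inputs from the protocol: up to five treatments, so four intervals, each 4 weeks with a margin of 2 weeks (2.7, 2.13). First to last treatment is 4 × 4 = 16 weeks at nominal spacing and 4 × 6 = 24 weeks at the longest.

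Assumed inputs: 50 to 100 women of childbearing potential among the 120 subjects, and contraceptive failure of 1% to 8% per year.

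Expected pregnancies conceived in the treatment period = women × (weeks / 52) × annual rate:

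- 16 weeks, low: 50 × 16/52 × 0.01 = 0.15
- 16 weeks, high: 100 × 16/52 × 0.08 = 2.5
- 24 weeks, low: 50 × 24/52 × 0.01 = 0.23
- 24 weeks, high: 100 × 24/52 × 0.08 = 3.7

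The range is 0.15 to 3.7. It supposes that all five treatments are given and that nobody leaves early. A conception in this period becomes an exposed pregnancy only if another treatment is given before it is detected.

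**3. What zero reports would tell**

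After zero birth defects in *k* pregnancies followed to outcome, the exact one-sided 95% upper bound on the risk is 1 − 0.05^(1/k):

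- k = 0: 100%, no information
- k = 1: 95%
- k = 3: 63%
- k = 6: 39%

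The chance of at least one report, with *m* pregnancies, true risk *q* and followed share *f*, is 1 − (1 − q·f)^m. With m = 3 and a range of assumed *q*:

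| q | all followed | half followed | none followed |
|---|---|---|---|
| 3% | 8.7% | 4.4% | 0% |
| 10% | 27.1% | 14.3% | 0% |
| 30% | 65.7% | 38.6% | 0% |

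The same true risk gives different chances of a report, depending only on how many Investigators chose to ask. That share is what the plan neither fixes nor records.

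**The case against.** The other side has several fair points.

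- **The Sponsor is not blind.** Every pregnancy that reaches the Investigator must be reported, and the Sponsor can then ask for its outcome. This stands: the missing piece is a duty to obtain the outcome, not knowledge of the pregnancy.
- **Few pregnancies are likely.** Section 2.3 excludes women of childbearing potential who do not use effective birth control and women planning a pregnancy. Section 2.6 allows extra tests, and Section 11.0 tells subjects to report a suspected pregnancy at once. This stands and keeps the point small.
- **Full follow-up would not give a useful rate.** Zero events in three pregnancies still leaves an upper bound of 63%. This also stands. The gain is in capturing and reporting individual serious events, not in estimating a risk.
- **The definition is generic.** Section 14.0 speaks of adverse device experiences, and Section 2.15 lists no reproductive effect among the known device effects. That lowers the prior expectation. However, Section 14.0 requires serious events to be reported whether or not they are judged related, so the plan does commit itself to reporting such an outcome.

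Two stronger readings are tempting. A reader might infer that zero reports would carry no information at all. That is true only if no pregnancy is followed, and Section 11.0 permits tracking. A reader might also count pregnancies over the full nine months, giving 50 × 0.75 × 0.01 = 0.4 to 100 × 0.75 × 0.08 = 6.0. But nine months is a ceiling, roughly 24 weeks of treatment plus 13 + 2 = 15 weeks to the latest date of an optional visit. A pregnancy conceived after the last treatment was not exposed to treatment.

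**Conclusion.** The point holds in a limited form. Following Sections 11.0, 12.0 and 14.0 exactly can leave a birth defect unseen although the protocol names it as a serious outcome. An absence of such reports cannot be interpreted unless the number of pregnancies and the number followed to outcome are stated with it.

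The size is small: about 0.15 to 3.7 pregnancies conceived during the treatment period. This rests on the assumed number of women and contraceptive failure rate, neither of which is in the documents. Safety is summarised without statistical comparison (2.16.6), and no success criterion (2.16.1), efficacy result or sample size changes. It is a cheap improvement to safety capture that is worth making.

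**What to change.** - **Section 11.0:** replace the optional wording on tracking with a duty, for example: *the Investigator will ask the subject's agreement to follow the pregnancy to outcome; the outcome will be recorded, and reported as a serious adverse event if it meets Section 14.0*. Keep the mandatory report of the pregnancy.
- **Section 12.0:** add to the sentence on data collection an exception for agreed pregnancy follow-up. Without it, the change to 11.0 would leave the two sections in conflict.
- **Section 14.0:** add the same exception to the sentence that ends adverse event reporting after resolution.
- **Section 2.16.6:** list each pregnancy in the safety summary with its timing relative to treatment and its outcome, or *outcome not obtained*, so that the number followed is visible.

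The cost is a sentence or a clause in each section, one listing and a few follow-up calls, some of them after the study's planned end. Follow-up would still depend on the subject's agreement, so some outcomes may stay unknown. The consent form is not in the review copy; confirm that it covers this contact, and add a sentence if it does not.
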